6.7 Sample Size Determination- Parent (Main) Study

For **Aim 1** we hypothesize that BAS+ vs. SC will have higher smoking abstinence rates and less PCWG at the 26-week follow-up (primary outcomes). Power calculations were all approximated as t-tests or z-tests, and conducted using PASS Software (Power and Sample Size, NCSS Software, Kaysville, UT), Bonferroni corrected for two primary outcomes ($p=.025$). Proportions of abstinent and smoking subjects will be compared using the log of the odds-ratio, which has a known variance. Informed by smoking cessation counseling plus TN research, we anticipate that the 6-month abstinence rate will be 13% in the SC (control) group and 25% in the BAS+ group (consistent with a persistent effect of BAS+ after the discontinuation of TN). A sample of 213 per group provides 82% power to detect this 12% difference in quit rates at 6 months. This represents a clinically meaningful effect and corresponds to a small effect size ($\delta=.15$). For PCWG, we will include all participants in the analysis, while testing a smoking status x treatment interaction. Informed by epidemiological and clinical studies of PCWG, we will have 80% power to detect a 6 pound (2.72 kg) difference in PCWG between BAS+ and SC, using the interaction term. We expect BAS+ vs. SC will have less post-cessation food intake (secondary outcome) at the 26-week follow-up. We have 80% power to detect a 320 kcal/day difference between the two groups ($p = .05$). In light of these considerations (i.e., 213 subjects per arm; total 426) and an attrition estimate of 15% across accrual, we will recruit a total of 245 subjects to each arm for a total of 490 subjects (~500).

For **Aim 2**, we hypothesize that BAS+ vs. SC, will increase alternative reinforcers, and reduce food reward, the RRVF, and food cue-induced craving. These changes, in turn, will predict less food intake and PCWG, and greater smoking abstinence at the 26-week follow-up. Using structural equation modeling, we will test the treatment effect on the slope of the mediators versus time, with pre-quit values representing the intercepts. We will examine the proportion of

CONFIDENTIAL

This material is the property of the University of Pennsylvania. Do not disclose or use except as authorized in writing by the study sponsor

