treatment effect explained, and test with a delta method generated z-score (Type I error of .05). There are four proposed mediating pathways between treatment and outcome, so our Type I error will be corrected to 0.0125. For smoking abstinence, a sample of 426 gives us 80% power to detect small effects ($\delta=0.32$) for changes in the proposed mediators, where serial observations are uncorrelated within subject. This also applies to individual path strength. Even a modest within-subject correlation ($\rho=0.3$) provides 80% power to detect a small treatment effect ($\delta=0.20$). For PCWG, smoking status will be treated as a time-varying covariate, where changes in weight are represented as a slope factor (based on observed repeated measures of weight). With a sample of 426, we will have power to detect a small effect ($\delta < 0.20$), even without adjustment for within-subject correlation.

As an **exploratory aim**, we will test whether females, or participants with greater pre-treatment depression symptoms, or weight concerns, are more likely to experience PCWG and more likely to benefit from BAS+ vs. SC. We will test an interaction effect predicting that the effects of the BAS+ will be more pronounced for females, and for those who have greater depression symptoms, or weight concerns. For smoking abstinence, with a 6-month quit rate difference of 12% (25% BAS+ vs. 13% SC), we approximated power by simulation using a z-test based on the ratio of odds ratio (ORR). If this effect, for example, is completely derived from a larger effect of BAS+ among females (no effect in males), then we will have 80% power to detect an interaction with 213 subjects per treatment arm. This corresponds to an odds ratio of ~4.0 for a BAS+ effect in females and an odds ratio of 1.0 in males. All tests will be performed at a $p < .05$ significance level. We approximated the same interaction for PCWG using the z-score. Restricting the sample to abstinent participants (54 BAS+, 28 SC) with continuous moderators dichotomized at the median, a standard deviation of 3.5 kg, and a standard error of 1.63 for the interaction, we will have 80% power to detect an interaction difference of 4.7 kg (10.4 lbs.).

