Aim 2 will involve assessing the direct effect of treatment on smoking cessation and PCWG, and the indirect or mediated effects of treatment on these outcomes through the hypothesized sequential mediating mechanisms using structural equation modeling. Mediation exists when a relationship between treatment and smoking cessation or PCWG is accounted for in full, or in part, by one or a set of intervening variables (e.g., alternative reinforcers, food cue-induced craving, food reward, RRVF). Longitudinal change in the mediators will be represented with a slope factor (based on observed repeated measures of each mediator). We will assess the mediation strength (absent to complete) by estimating the effect proportion mediated ($\beta_{\text{indirect}}/\beta_{\text{total}}$), and determine the significance of effects with Delta method standard errors, with bootstrapped standard errors for validation. We will employ a weighted least squares estimation technique with robust standard errors, and a mean and variance adjusted chi-square test for the estimation of model parameters. Multiple indicators of model performance will be used, including the χ^2 test, Comparative Fit Index ($< .95$), Weighted ($<.90$) and Standardized Root Mean Square Residual ($<.80$), Root Mean Squared Error of Approximation ($< .05$), and an examination of standardized model residuals. Bayesian Information Criterion and Scaled Unit Information Prior BIC will be used to compare different models.

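### The two Aim 2 mediator power figures in section 6.7 (delta = 0.32 at rho = 0 and delta = 0.20 at rho = 0.3) do not come from any one standard model examined, and the 0.20 is not shown for the planned slope test

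*Combined protocol and SAP*

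**What the plan says.** Section 6.7 names the Aim 2 test: "we will test the treatment effect on the slope of the mediators versus time, with pre-quit values representing the intercepts". Section 6.10 agrees: "Longitudinal change in the mediators will be represented with a slope factor". With four mediating pathways, section 6.7 adds "so our Type I error will be corrected to 0.0125".

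Two power statements follow, differing only in the assumed within-subject correlation. With uncorrelated serial observations, a sample of 426 "gives us 80% power to detect small effects", given as delta = 0.32. With rho = 0.3, the same sample "provides 80% power to detect a small treatment effect", given as delta = 0.20.

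The only description of method is the general remark in the same section: "Power calculations were all approximated as t-tests or z-tests". The scale of delta, the correlation structure, the number of measures and the handling of the intercept are not stated. Sections 3.4 and 4.2 now plan for about 340 participants, not 426.

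**The concern.** Moving from 0.32 to 0.20 means cutting the variance to (0.20/0.32)² = 0.39 of its former value. A correlation of 0.3 would not be expected to do that in a slope test, so the two figures look as if they came from different calculations.

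The treatment effect on these mediators is hypothesis H2a, and the claim that Aim 2 can detect a small effect of 0.20 rests on this sentence. If the figure does not belong to the planned test, the sensitivity of Aim 2 is unknown and may be overstated.

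**Working it through.** **Inputs.** 213 per arm, alpha .0125 and 80% power (section 6.7). Two-sided testing is assumed, because sidedness is not stated for the parent study; exchangeable correlation is assumed, because no structure is given. From section 6.5.4, cue craving, food reward and RRVF are measured at weeks -2, 1, 4 and 8, and alternative reinforcers (PES) at weeks -2, 1, 2, 4 and 8.

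**Formulas.** Let f be the variance factor relative to one value per subject.
- Detectable delta = (2.498 + 0.842) × sqrt(2f/213) = 0.324 × sqrt(f)
- Power = Φ(delta / (0.0969 × sqrt(f)) − 2.498)

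**1. The 0.32.** One value per subject (f = 1) gives a detectable delta of 0.324, with 78.9% power at 0.32. It reproduces.

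**2. The 0.20.** This needs f = (0.20/0.324)² = 0.382. A mean of k post-baseline values adjusted for one baseline has f = (1 + (k−1)rho)/k − rho².

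| k | rho | f | Detectable delta | Power at 0.20 |
|---|---|---|---|---|
| 4 (PES) | 0.3 | 1.9/4 − 0.09 = 0.385 | 0.201 | 79.6% |
| 3 (other mediators) | 0.3 | 1.6/3 − 0.09 = 0.443 | 0.215 | 72.6% |
| 4 | 0 | 0.250 | 0.162 | – |
| 3 | 0 | 0.333 | 0.187 | – |

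So 0.20 reproduces for PES only, and the same model at rho = 0 gives 0.16, not 0.32. In this model correlation raises the detectable effect, the opposite of what section 6.7 describes.

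**3. Slope test scaled from the plan's own 0.32.** With free intercepts and exchangeable correlation, rho multiplies the slope variance by (1 − rho). Then 0.324 × sqrt(0.7) = 0.271, and power at 0.20 is Φ(0.20/(0.0969 × 0.837) − 2.498) = 49%. Reaching 0.20 would need rho of about 0.61-0.62.

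**4. Slope test computed directly, with delta as the week-8 difference in single-occasion SDs.** With free intercepts f = (1 − rho) × T²/Sxx, where T = 10 weeks. For weeks -2, 1, 4, 8 the mean is 2.75 and Sxx = 54.75, so T²/Sxx = 1.826; for PES Sxx = 55.2, giving 1.812. The common-baseline rows are the generalized least squares slope with one intercept shared by both arms.

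| Model | Visits | Detectable delta, rho = 0 | Detectable delta, rho = 0.3 | Power at 0.20, rho = 0.3 |
|---|---|---|---|---|
| Free intercepts | 4 | 0.437 | 0.366 | 25% |
| Free intercepts | 5 (PES) | 0.436 | 0.364 | 25% |
| Common baseline | 4 | 0.269 | 0.289 | 43% |
| Common baseline | 5 (PES) | 0.255 | 0.287 | 43% |

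Simulation of the free-intercept slope gave 26%.

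**5. Slope test with delta as the mean post-baseline difference.** A linear divergence averages 6.33/10 of its week-8 value over the three post visits and 5.75/10 over the four PES visits, so f is multiplied by the square of that ratio. Power at 0.20 with rho = 0.3 is then about 65% (PES 75%) with free intercepts and 88% (PES 94%) with a common baseline. The detectable delta at rho = 0 is 0.28 (PES 0.25) and 0.17 (PES 0.15) respectively, so none of these gives 0.32.

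**6. Sensitivity.** At uncorrected alpha .05, step 3 gives 69% and free intercepts in step 4 gives 45%. With AR(1) correlation, the step 4 models give 15-41%. A wider scan covered means, change scores, baseline-adjusted means with 1-3 pre and 1-10 post values, and both kinds of slope, at alphas .05, .025, .0125 and .00625, one- and two-sided. No model put both stated figures within 2 points of 80%.

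**7. At 340.** The multiplier is sqrt(426/340) = 1.119. On the week-8, free-intercept scale this gives 0.437 × 1.119 = 0.49 at rho = 0 and 0.366 × 1.119 = 0.41 at rho = 0.3.

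**The case against.** The plan says its power was approximated with t- or z-tests and does not claim to derive it from the structural equation model. Taken alone, 0.20 is a fair approximation for a repeated-measures mean: 79.6% for PES and 73% for the other mediators, a shortfall of 0-7 points. This stands for the single figure. It does not rescue the pair, because the same approximation gives 0.16 at rho = 0.

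A reader might infer that Aim 2 simply has 25-49% power under the named test. The documents do not support that unconditionally. Delta is undefined, and having the pre-quit values represent the intercepts leaves a baseline-anchored slope arguable. Across the readings in steps 4 and 5, power at 0.20 runs from 25% to 94%. Nor is the sqrt(1 − rho) shrinkage general: with a common baseline, correlation slightly raises the detectable effect.

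A reader might also want to write 0.27 in place of 0.20. That would repeat the fault, since 0.27 multiplies a single-value figure by a factor that belongs to slopes; the free-intercept slope on the week-8 scale already needs 0.44 at rho = 0.

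Finally, nothing in the documents says that null paths will be read as absence of mediation. Section 6.10 plans an estimated proportion mediated with Delta-method and bootstrapped standard errors.

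**Conclusion.** The concern holds as an inconsistent pair of figures that is not tied to the planned test. Each can be reproduced alone, but from different models. This is shown for the standard families examined, not proved for every possible model.

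How far power falls short at 0.20 depends on what delta means. It is about 49% if 0.32 is accepted as the free-intercept slope test at rho = 0, and about 25% or 43% on the week-8 scale with exchangeable correlation. On a post-baseline-mean scale it is 65-94%, a reading that contradicts the plan's own 0.32. All these values assume two-sided alpha .0125 and N = 426. The defect is that section 6.7 does not say which reading applies, so its claim of 80% power at 0.20 cannot be relied on.

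**What to change.** In section 6.7, replace both Aim 2 figures with detectable effects from one stated model, the planned slope test. State the scale of delta, the visits used for each mediator, the intercept handling and the correlation structure, and use the same model for both values of rho. For example, with delta as the week-8 difference in single-occasion SDs, free intercepts and exchangeable correlation, N = 426 gives 0.44 at rho = 0 and 0.37 at rho = 0.3. Restate the figures for the roughly 340 participants now planned: about 0.41 at rho = 0.3 on that scale.

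The cost is a less favourable stated figure. Neither the sample size nor the conduct of the trial changes.

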6.8 Sample Size Determination - Neuroimaging Sub-Study

We plan to test hypotheses at a global 5% Type I error (alpha) for each family of hypotheses, and have chosen a completed sample ($N=60$) that will achieve at least 80% power using 2-sided tests. Our analysis of power was based on “effect size” (standardized difference). Effect sizes were calculated from our own preliminary data, from published data summaries, and from published estimates of effects (e.g., t statistics, coefficients, p-values) using validated summary methods. We have several hypotheses and more than one outcome measure for some (e.g., different brain regions). We will control error in a family-wise manner, adjusting alpha (Bonferroni Aims 1 and 2, Hochberg step-up procedure for Aim 3) for the number of tests within each hypothesis family. Bonferroni corrections will also be adjusted for the correlations among multiple outcomes.

Aim 1 includes 2 hypotheses (**H1a&b**) regarding treatment effects on neural responses including 5 ROIs responding to food-related tasks. We test at $p<0.02$ because of the high correlation among ROIs within subjects ($\rho=0.54$). Estimates of effect size from our center data ($d=0.36$) indicate that we have 80% power to detect the effects. Aim 1 also tests hypothesis **H1c** for cessation effects. At the Bonferroni corrected threshold of $p=0.0167$, we have 80% power to detect small to medium effect sizes ($d=0.37$).

Aim 2 (H2a&b) essentially tests for mediation. The hypothesis that cessation increases food intake will be tested at 0.05, with power for effect sizes $\sim d=0.32$ [9, 58]. For Aim 2b (ROIs predicting food intake), we expect a weaker correlation than H1a ($\rho=0.4$), and our adjusted threshold for significance is $p<0.01$. Expected effect sizes are approximately 0.5, and we expect 96% power to detect the effects.

Aim 3 begins with the model in Aim 2b above, and tests interacting effects of working memory-related BOLD signal and food reinforcement (or food cue reactivity) on food intake. We will reduce the complexity of this analysis by using difference scores (pre minus post) to model a 2-

CONFIDENTIAL

This material is the property of the University of Pennsylvania. Do not disclose or use except as authorized in writing by the study sponsor

way interaction between working memory and food reinforcement on food intake. We will only test for brain ROIs found to be sensitive to treatment in Aim 1, the number of tests for interaction is uncertain. We anticipate that these effects will be positively correlated and will use the Hochberg step-up procedure, which is robust to correlations among outcomes in the range we expect. For purposes of power calculation, we assumed a correlation of 0.5, which resulted in a corrected p-value of 0.02 for 5 tests. Keeping the independent variables continuous, we can detect an interaction term (one-sample per subject, standardized) of $d=0.36$ with 80% power. Literature estimates for similar interactions were 0.65, 0.66, and 0.35. The lowest estimate gives 77% power, and the average (0.55) yields 98% power.

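### Testing five Aim 1 ROIs at p<0.02 does not hold the promised global 5%: as one family correlated at 0.54, the family-wise error is about 7.8%

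*Combined protocol and SAP*

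**What the plan says.** All the inputs stand in section 6.8 (Sample Size Determination - Neuroimaging Sub-Study).

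- Error target: "We plan to test hypotheses at a global 5% Type I error (alpha) for each family of hypotheses", with a sample size "that will achieve at least 80% power using 2-sided tests".
- Method: control is family-wise, "adjusting alpha (Bonferroni Aims 1 and 2, Hochberg step-up procedure for Aim 3) for the number of tests within each hypothesis family". The section adds: "Bonferroni corrections will also be adjusted for the correlations among multiple outcomes". It gives no formula for that adjustment.
- Aim 1: two hypotheses (H1a and H1b) "regarding treatment effects on neural responses including 5 ROIs responding to food-related tasks".
- Threshold: "We test at $p<0.02$ because of the high correlation among ROIs within subjects", with the correlation given as 0.54.
- Aim 2b: threshold 0.01, at an expected correlation of 0.4.
- Aim 3: the decision rule is Hochberg. For the power calculation only, a correlation of 0.5 is taken to give a corrected p-value of 0.02 for five tests.

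Other sections count the regions differently. Section 2.2 lists four regions for H1a (insula, ACC, OFC, VS/NAC) and two for H1b (VS/NAC, vmPFC): five distinct regions but six region-by-task tests. Section 6.11 names two primary ROIs for the cue and reinforcement tasks (VS and ventromedial PFC) and makes OFC and insula secondary.

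**The concern.** Plain Bonferroni for five tests is 0.05/5 = 0.01. Section 6.8 doubles this on the strength of a correlation of 0.54. Positive correlation does allow some relaxation, but for two-sided tests the gain is small until the correlation is very high. A factor of two at 0.54 therefore looks too generous.

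At stake is the decision threshold for the sub-study's first aim, which would not have the error rate claimed for it. The consequence carries forward, because Aim 3 tests only the ROIs found sensitive to treatment in Aim 1, so a loose threshold passes extra regions on. The power stated at 0.02 is also higher than the same design would give at a threshold that holds 5%.

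**Working it through.** **Inputs (section 6.8):** K = 5 tests, two-sided, family-wise target 0.05, per-test threshold 0.02, correlation 0.54. Two assumptions are added: the five tests are one family, and 0.54 is the common correlation of the test statistics.

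**Step 1. Can 0.02 be reproduced as a threshold holding 5%?**

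| Method, K = 5, correlation 0.54 | Per-test threshold |
|---|---|
| Bonferroni, 0.05/5 | 0.0100 |
| Exact, equicorrelated normal, two-sided | 0.0124 |
| Effective number of tests from eigenvalues, 0.05/3.83 (Nyholt) | 0.0130 |
| Exact, one-sided | 0.0132 |
| Effective number of tests from eigenvalues, 0.05/3 (Li-Ji) | 0.0167 |
| 0.05/5^(1-0.54) = 0.05/2.10 | 0.0238 |

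None equals 0.02. The last two round to it, but both exceed the exact value of 0.0124, so neither holds 5% here.

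**Step 2. Family-wise error at 0.02.** The critical value is c = 2.326. With Z_i = √ρ·X + √(1-ρ)·e_i,

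FWER = 1 - ∫ φ(x) [Φ((c-√ρ x)/√(1-ρ)) - Φ((-c-√ρ x)/√(1-ρ))]^K dx.

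For K = 5:

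| Correlation | FWER at 0.02 |
|---|---|
| 0 | 9.6% |
| 0.50 | 8.0% |
| **0.54** | **7.8%** |
| 0.70 | 6.6% |
| 0.80 | 5.6% |
| about 0.85 | 5.0% |

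Simulated two-sample t-tests at correlation 0.54 agree: 7.8% at N = 60 and 7.9% at N = 50.

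**Step 3. Sensitivity.**

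- *Rounding.* The smallest value that prints as 0.02 is 0.015, and it gives 5.95%.
- *Unequal correlations.* Three structures with blocks of three and two regions, each averaging 0.54, gave 7.0%, 7.5% and 7.6%.
- *One-sided tests.* One-sided testing at 0.02 gives 7.3%.
- *Family size*, at common correlation 0.54:

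| Tests in family | FWER at 0.02 | Threshold holding 5% |
|---|---|---|
| 2 | 3.7% | 0.0273 |
| 3 | 5.2% | 0.0192 |
| 4 | 6.5% | 0.0150 |
| 5 | 7.8% | 0.0124 |
| 6 | 8.9% | 0.0106 |

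**Step 4. Effect on power.** Take 80% at 0.02 as true. The standardised shift is 2.326 + 0.842 = 3.168.

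- At 0.0124 the critical value is 2.501: Φ(3.168 - 2.501) = Φ(0.667) = 75%.
- At 0.01 it is 2.576: Φ(3.168 - 2.576) = Φ(0.592) = 72%.

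**The case against.** The strongest objection is that the documents do not fix the family. Section 6.8 controls error within each family and names two hypotheses. If section 6.11's two primary ROIs are one task's family, 0.02 gives 3.7% and the promise is kept. This stands in part: 7.8% is conditional and should not be quoted as an unconditional property of the plan. It does not rescue the threshold, because section 6.8 ties 0.02 explicitly to five ROIs, and every family of three to six tests exceeds 5%. If two tests were meant, sections 6.8 and 6.11 conflict.

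A second objection is that a single common correlation is assumed. That also stands, and it is why 0.0124 is not the one correct threshold. The unequal structures lower the error only to 7.0%.

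Third, BOLD signal is a secondary outcome of the sub-study (section 1.2), and nothing here touches the parent trial's primary tests. This limits the importance of the point but does not change the arithmetic.

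Two stronger readings are tempting and not supported:

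- *That 0.02 came from a particular shortcut.* A reader might infer 0.05/m^(1-ρ), which rounds to 0.02 at 0.54. The documents name no formula. With five tests at correlation 0.4 the shortcut would give 0.019, where Aim 2b has 0.01, and an effective-number method (0.0167) rounds to 0.02 as well.
- *That Aim 3 is tested at the wrong level.* Its 0.02 is a power-calculation input; the decision rule is Hochberg.

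Nor can Aim 2b's 0.01 be certified outright. It gives 4.5% at correlation 0.4 if that family has five tests, but no count is stated.

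**Conclusion.** The point holds in conditional form. With the five Aim 1 ROIs as one family of two-sided tests at a common correlation of 0.54, testing each at 0.02 gives a family-wise error of about 7.8% against a stated 5%. Unequal correlations averaging 0.54 gave 7.0% to 7.6%, and families of three to six tests give 5.2% to 8.9%. Only a two-test family, at 3.7%, is within the limit, and section 6.8 does not describe one. The common correlation would have to be about 0.85 for 0.02 to hold 5% over five tests.

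The Aim 3 power figure rests on the same step: 0.02 for five tests at correlation 0.5 corresponds to 8.0%. This is a correction the plan should make. It concerns a sub-study's mechanistic endpoints.

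The power loss in Step 4 takes the stated 80% as given. The power model is not described, and simple z-tests for d = 0.36 at 0.02 with N = 60 gave 68% (one-sample) and 18% (two-sample).

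**What to change.** 1. Define the Aim 1 ROI family once, with the number of tests and whether H1a and H1b are one family or two, and make sections 2.2, 6.8 and 6.11 agree.
2. Replace 0.02 with a rule that holds 5% for that family. For five tests the options are:
   - the Hochberg step-up already planned for Aim 3, whose thresholds need no correlation estimate;
   - plain Bonferroni at 0.01, which needs no correlation assumption;
   - about 0.012, stated as conditional on a common correlation of 0.54.

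   If any correlation adjustment is kept, write out its formula.
3. Restate Aim 1 power under the chosen rule, with the power model described.
4. Restate the Aim 3 power figure without 0.02. For five tests at correlation 0.5 the threshold holding 5% is 0.0120. Aim 3's Hochberg decision rule can stay as it is.

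The cost is a slightly stricter threshold and lower stated power, about 75% or 72% instead of 80%. It is a text change that needs no new data and adds no burden for participants.

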3.2 General Design - Neuroimaging Sub-Study

We propose to study a sub-sample of consecutively recruited participants (N=~50) enrolled in the parent randomized clinical trial. As displayed in **Figure 2**, an equal number of fMRI eligible smokers from the BAS+ or SC treatment group will be studied before treatment (~week -2) and during the final week of nicotine patch therapy (~week 7-8). As part of the parent study, smoking will be assessed by self-report and biochemically confirmed weekly after quitting, at EOT (week 8), and at the 12 and 26 week follow-ups. Weight will be assessed at these same time points. Food intake will be measured by three consecutive days of 24-hour food recalls at baseline and 4-, 8-, 12- and 26-weeks post-TQD.

Scans identified in **Figure 2** and included within the Study Procedures Section represent approximations. Participants will complete scans as designated in Figure 2 and the Study Procedures, but will be permitted a degree of flexibility at the discretion of the Principal Investigator due to extenuating circumstances.

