3.5 Study Duration- Neuroimaging Sub-Study

Recruitment/enrollment for the neuroimaging sub-study is anticipated to begin in late July or August 2017 and will continue for ~18 months. We estimate that up to 50 participants will have completed the neuroimaging sub-study by ~April 2019. We estimate that it will take ~10 weeks/2.5 months for a participant to complete the neuroimaging sub-study (i.e. both fMRI scans).

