4.3 Accrual - Neuroimaging Sub-Study

Eligible participants enrolled in the parent study who meet the fMRI eligibility criteria will have the opportunity to participate in the neuroimaging sub-study. We estimate that in order to achieve a sample of ~50 participants who complete the neuroimaging sub-study with usable data, we will need to enroll ~75 participants into the sub-study. Accrual estimates are based on our extensive experience conducting neuroimaging studies and specifically recruitment of fMRI subsamples from larger clinical trials. To ensure retention, we: (1) educate subjects about the benefits of participation and knowledge gained from the study; (2) schedule sessions at convenient times; (3) provide reminder calls; and (4) provide incentives for completion of sessions and assessments. This accrual rate is highly feasible based on our prior work.

CONFIDENTIAL

This material is the property of the University of Pennsylvania. Do not disclose or use except as authorized in writing by the study sponsor

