Aim 1: Identify effects of BAS+ (vs SC) treatment on food related neural activity and behavior: These comparisons are all between subject, and will be analyzed using mixed models regression (xtmixed, StataCorp, Texas). The model predictors will include a binary indicator for group (BAS+ vs. SC). The hypothesis will be tested using the z-score corresponding to the main effect of group. Covariates can be included in the model to control error (sex, BMI, nicotine dependence, age, weight concerns), although we do not expect to make large gains for adding subject-level controlling variables in a mixed model.

Aim 2: Evaluate the relative contribution of these neural processes to post-cessation caloric intake: Our outcome variable is average daily calories based on food recalls. The first comparison (pre vs. post-treatment) is within-subject, and will be analyzed using mixed models regression with subject specific random effects. As before, we include a binary predictor for condition, a categorical indicator for serial day, and we will test using the z-score corresponding to condition. For testing candidate mediators, we will again model calories using mixed models, entering variables as time-varying (condition varying) predictors, along with subject specific random effects. Finally, we will build the larger model, looking for confounding that represents potential mediation. For this purpose, we will use regression-based multi-equation path models. Path Analysis partitions a directly measured bivariate relationship, for example, between abstinence and calories ingested, into direct and indirect causal paths, to tease apart the important components mediating the response. We will deem that mediation has occurred when a relationship between abstinence and food intake accounted in full, or in part, by one or more of the intervening variables (BOLD signal change or subjective responses in cessation vs. smoking). We will assess the strength of the indirect effects through confidence intervals, evaluate the proportion mediated (i.e., partial or complete mediation), and determine significance with Delta method standard errors. To assess the level of mediation for a pathway, we will estimate the ratio of the indirect effect to the total effect (i.e., effect proportion mediated $\beta_{\text{indirect}}/\beta_{\text{total}}$).

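### The neuroimaging sub-study bases its power on 60 completers but plans about 50, and the 80% stated for Aim 1 is not supported for the between-arm test it will use

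*Combined protocol and SAP*

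**What the plan says.** Section 6.8 says the investigators "have chosen a completed sample ($N=60$) that will achieve at least 80% power using 2-sided tests". It measures effects as standardized differences and lists these cases:

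- Aim 1, H1a and H1b: d=0.36 at p<0.02. "Estimates of effect size from our center data ($d=0.36$) indicate that we have 80% power to detect the effects".
- Aim 1, H1c: d=0.37 at p=0.0167, 80% power.
- Aim 2: d of about 0.32 at 0.05. No separate power figure is given, so the general 80% target applies.
- Aim 2b: d of about 0.5 at p<0.01, 96% power.
- Aim 3: d=0.36 at 0.02 with 80% power, described as one sample per subject. For the literature estimates, "The lowest estimate gives 77% power, and the average (0.55) yields 98% power". The lowest estimate is 0.35.

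The other sections plan a smaller sample:

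- Section 3.2: "We propose to study a sub-sample of consecutively recruited participants (N=~50) enrolled in the parent randomized clinical trial", with equal numbers from each arm.
- Section 3.5: "We estimate that up to 50 participants will have completed the neuroimaging sub-study by ~April 2019".
- Section 4.3: about 75 are to be enrolled "in order to achieve a sample of ~50 participants who complete the neuroimaging sub-study with usable data".

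Section 6.11 says of Aim 1: "These comparisons are all between subject, and will be analyzed using mixed models regression". It adds: "The hypothesis will be tested using the z-score corresponding to the main effect of group".

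**The concern.** There are two separate problems.

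First, the completed N in the power section disagrees with the design, duration and accrual sections, which agree with one another. Power claimed at 60 does not carry over to 50.

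Second, the Aim 1 test compares two groups of 25 to 30. A standardized difference of 0.36 is small for groups of that size, and the plan does not say which comparison the figure describes. Some of the text points to a within-subject basis. Section 6.8 calls H1c a cessation effect, although section 2.2 defines it as BAS+ versus SC, and it labels the same d=0.36 with 80% power as one-sample under Aim 3. This is suggestive, not conclusive.

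The stake is how Aim 1 is interpreted. A null result would be set against a stated 80% power that the planned test is not shown to have. Aim 1 also limits Aim 3, because section 6.8 carries forward only the brain regions found sensitive to treatment in Aim 1.

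**Working it through.** **Inputs.** The d values, alphas and N=60 come from section 6.8. N=50 comes from sections 3.2, 3.5 and 4.3, and equal allocation from 3.2. The between-arm test comes from 6.11. All tests are two-sided.

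**Step 1: reproduce the stated figures as one-sample tests.** The normal approximation is power = Φ(d√N − z), with z the 1−α/2 normal quantile. The exact version uses the noncentral t with N−1 degrees of freedom.

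For Aim 1 at N=60: 0.36×√60 = 2.789; 2.789 − 2.326 = 0.462; Φ = 67.8% (exact t 65.5%). At N=50: 0.36×√50 = 2.546; 2.546 − 2.326 = 0.219; Φ = 58.7% (exact t 55.9%).

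| Case | d, alpha | Stated | N=60 (t / normal) | N=50 (t / normal) |
|---|---|---|---|---|
| Aim 1 H1a, H1b | 0.36, 0.02 | 80% | 65.5 / 67.8% | 55.9 / 58.7% |
| H1c | 0.37, 0.0167 | 80% | 65.7 / 68.2% | 55.8 / 58.8% |
| Aim 2 | 0.32, 0.05 | 80% target | 68.4 / 69.8% | 60.2 / 61.9% |
| Aim 2b | 0.5, 0.01 | 96% | 88.2 / 90.3% | 79.9 / 83.1% |
| Aim 3, lowest | 0.35, 0.02 | 77% | 62.6 / 65.0% | 53.2 / 55.9% |
| Aim 3, average | 0.55, 0.02 | 98% | 96.7 / 97.3% | 92.7 / 94.1% |

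Only the last row comes close to its stated value, and only at N=60.

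**Step 2: look for a route to the stated figures.** Two come close, and section 6.8 describes neither.

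*Averaging two observations per subject at rho=0.54.* The variance factor is (1+0.54)/2 = 0.77, so the effective N is 60/0.77 = 77.9 or 50/0.77 = 64.9. The formulas of step 1 are then applied to the effective N.

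| Case | Stated | N=60 (t / normal) | N=50 (t / normal) |
|---|---|---|---|
| Aim 1 H1a, H1b | 80% | 78.7 / 80.3% | 69.6 / 71.7% |
| H1c | 80% | 79.2 / 80.9% | 69.9 / 72.2% |
| Aim 2 | 80% target | 79.7 / 80.6% | 71.9 / 73.2% |
| Aim 2b | 96% | 95.9 / 96.7% | 91.1 / 92.7% |
| Aim 3, lowest | 77% | 76.1 / 77.7% | 66.8 / 68.9% |

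Section 6.8 uses other correlations for two of these aims. With its 0.4 for Aim 2b, N=50 gives 93.9 / 95.1%. With its 0.5 for Aim 3, N=50 gives 68.2 / 70.2%.

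*A one-sample test at N=75, the enrolment figure.* By the normal approximation this gives 78.6% (Aim 1), 79.1% (H1c), 79.1% (Aim 2), 96.0% (Aim 2b) and 76.0% (Aim 3, lowest). Enrolled participants are not completers, so this cannot support the claim.

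**Step 3: the between-arm test planned for Aim 1, if d=0.36 is a between-arm difference.** With n per arm, the noncentrality is d√(n/2) on 2n−2 degrees of freedom. For 25 per arm it is 0.36×√12.5 = 1.273; for 30 per arm, 0.36×√15 = 1.394. The plan gives no pre-post correlation r, so the values below are assumptions. Adjusting for baseline multiplies the variance by 1−r², so d becomes d/√(1−r²). Exact t, alpha 0.02:

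| Assumed r | 25 per arm | 30 per arm |
|---|---|---|
| 0 (unadjusted) | 13.8% | 16.7% |
| 0.5 | 18.5% | 22.5% |
| 0.8 | 39.6% | 47.7% |
| 0.9 | 69.5% | 78.7% |

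Reaching 80% needs r = 0.921 at 25 per arm or 0.903 at 30 per arm. Without adjustment, the normal approximation requires 155 per arm.

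**Step 4: effect detectable with 80% power between arms at alpha 0.02.** At 25 per arm: 0.922 (r=0), 0.799 (r=0.5), 0.553 (r=0.8). At 30 per arm: 0.838, 0.725, 0.503.

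**The case against.** The strongest reply is that the arithmetic in section 6.8 may be sound at N=60. Averaging two observations at rho=0.54 reproduces five figures across four alpha levels to within about a point. That looks like one consistent but unstated repeated-measures assumption. On that route the loss from 60 to 50 is small for Aim 2b: about 94–95% against 96%, using the plan's own correlation of 0.4.

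This stands in part. The fault at N=60 may be an unstated assumption and not a miscalculation. But section 6.8 gives 0.54 as the correlation among brain regions, used to justify the p<0.02 threshold, and it calls Aim 3 one-sample. The N=75 route fits about as well, so neither is established. Even on the averaging route, Aim 1 falls to 70–72% at the planned 50. The route also says nothing about a comparison of arms.

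The between-arm percentages are conditional: they apply only if d=0.36 is a between-arm difference, and the adjusted values rest on assumed correlations. The adjusted rows may also be generous, because the covariates listed in section 6.11 do not include baseline BOLD signal. The other reading does not rescue the claim, since it leaves the planned contrast with no effect size.

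Finally, this is a mechanistic sub-study projected to finish by about April 2019, and this protocol version carries text dated after 30 March 2020 (section 6.2.11). The correction is therefore probably retrospective. It still affects how the results can be reported.

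**Conclusion.** The concern holds. The conflict between 60 and about 50 completers is plain in the text, and nothing in the documents resolves it. For Aim 1 at the planned N, the stated 80% is not reached at the stated two-sided alpha under any reading tried: 56–59% one-sample, 70–72% with two averaged observations, and about 14% between arms without adjustment. The between-arm figure rises to about 40% at an assumed pre-post correlation of 0.8 and reaches 80% only near 0.92. If d=0.36 is within-subject, the planned contrast has no supported power figure at all.

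Confidence is high on the N mismatch and on the missing between-arm effect size. The between-arm percentages depend on how d is read and on the assumed correlation. Aim 3 is stated as one-sample, so only the N problem and the undescribed method apply to it. The parent trial's primary outcomes are not affected.

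**What to change.** 1. Give one completed N in sections 3.2, 3.5, 4.3 and 6.8.
2. For each d in section 6.8, say whether it is within-subject or between-arm, whether it is on the raw or change scale, and whether observations are averaged. If they are, give the number and the correlation.
3. Restate Aim 1 power, or the detectable effect, for the between-arm test in section 6.11. At p<0.02 and 80% power without adjustment, the detectable d is about 0.92 at 25 per arm or 0.84 at 30 per arm. If baseline adjustment is intended, add it to the model in 6.11 and state the correlation assumed. At 25 per arm the detectable d is then about 0.80 for r=0.5 and 0.55 for r=0.8.
4. Recompute the H1c, Aim 2, Aim 2b and Aim 3 figures at the same N.

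The cost is protocol wording only; accrual and scanning do not change. The stated power will be much less favourable, and a null Aim 1 result would then need to be reported with its confidence interval and the restated detectable effect.
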